2.3.3 ADJUSTMENTS FOR MULTIPLICITY

The hypothesis tests for two primary endpoints will be considered independently without adjustment for multiplicity since both tests must reach significance for the study to successfully support the clearance of the balloon device. If both endpoints reach success for the study as outlined below, then three analyses will be performed for consideration in labeling by testing for the superiority of the balloon to the *Control Group*.

- The primary safety endpoint will be evaluated using a two-sided Fisher's Exact test in order to assess superiority of the balloon safety.
- The secondary endpoint rate of Grade 2 or greater rectal adverse events or implantation procedure related adverse events with a duration of at least 5 days will be evaluated using a two-sided Fisher's Exact test.
- The secondary endpoint of the degree of all GU acute toxicity as determined by the Expanded Prostate Cancer Index Composite (EPIC) at the last day of IMRT will be evaluated using a two-sided Rank-Sum (Wilcoxon) test.

The additional endpoints will be evaluated using two-sided tests. If any of these should reach significance at the 0.0167 level, then the results would be considered to be supportive of an additional claim or claims (e.g. a Bonferroni will be used to control for multiplicity).

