### **10.2** Adjustments for Multiplicity of Endpoints

The study has two co-primary endpoints. Each co-primary endpoint will be tested using one-sided alpha equal to 0.025 tests. To control the overall type I error, both co-primary hypotheses must be met to declare success on the primary analysis.

If both co-primary endpoints reach success for the study, then the following three secondary analyses will be performed for consideration in labeling by testing for the superiority of ProSpace to the control:

- The primary safety endpoint will be evaluated using a two-sided Fisher's Exact test in order to assess superiority of ProSpace safety.
- The secondary endpoint rate of Grade 2 or greater rectal adverse events that are also devicerelated, marking/implantation procedure-related, or IMRT-related with a duration of at least 5 days will be evaluated using a two-sided Fisher's Exact test.

The additional endpoints will be evaluated using two-sided tests. The secondary analyses will control for multiplicity to maintain an overall Type I error rate of 0.05. If any of these should reach significance at the 0.0167 level, then the results would be considered supportive of an additional claim or claims (i.e., a Bonferroni will be used to control for multiplicity).

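### Holm's step-down in place of a fixed 0.0167 would add a little power for second and third labelling claims at the same 0.05 familywise error, once the list of tests is settled

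*SAP*

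**What the plan says.** Both documents place the superiority tests behind success on both co-primaries. SAP 10.2 says "then the following three secondary analyses will be performed for consideration in labeling" and sets the aim: "The secondary analyses will control for multiplicity to maintain an overall Type I error rate of 0.05". The tests are two-sided ("The additional endpoints will be evaluated using two-sided tests"), each is judged against 0.0167, and the SAP names the method: "a Bonferroni will be used to control for multiplicity". Protocol 2.3.3 has the same threshold ("If any of these should reach significance at the 0.0167 level") and the looser wording "e.g. a Bonferroni will be used to control for multiplicity". Neither document gives a step-down rule.

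The lists of tests differ:

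- Protocol 2.3.3 lists three: superiority on the primary safety endpoint (Fisher), Grade 2 or greater events lasting at least 5 days (Fisher), and EPIC genitourinary toxicity on the last IMRT day (Wilcoxon).
- SAP 10.2 announces three but lists two. The first is "The primary safety endpoint will be evaluated using a two-sided Fisher's Exact test in order to assess superiority of ProSpace safety". The second begins "The secondary endpoint rate of Grade 2 or greater rectal adverse events that are also". The EPIC test is absent.

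Power is stated for the co-primaries only (Protocol 2.3.4.4, SAP 6).

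**The concern.** A single-step Bonferroni rule holds every test to 0.05/3 whatever the other tests show. Holm's procedure orders the p-values and compares the smallest with 0.05/3, the next with 0.05/2 and the largest with 0.05, stopping at the first failure. Both rules meet the SAP's 0.05 aim under any dependence between the tests. Holm's first step is the Bonferroni threshold and its later steps are wider, so it cannot lose a claim that Bonferroni would win.

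At stake is some power for second and third superiority claims against the randomised control. Study success and sample size are not affected.

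**Working it through.** **1. The plan's figure.** 0.05/3 = 0.01667, which rounds to 0.0167. For three independent tests the familywise error is 1 − (1 − 0.05/3)³ = 0.049. The bound 3 × 0.0167 = 0.0501 exceeds 0.05 only through rounding.

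**2. Error control under Holm.** In 1,000,000 simulated trials per scenario with all three nulls true, familywise error was 0.049 for both rules at correlation 0 and 0.044 for both at correlation 0.5. In no simulated scenario did Bonferroni reject a hypothesis that Holm kept.

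**3. Test 1 at the documents' own rates.** Inputs: 19% balloon, 21% control, 136 and 68 evaluable (Protocol 2.3.4.4, SAP 6). Exact enumeration of the two-sided Fisher test:

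| Level | 0.0167 | 0.025 | 0.05 |
|---|---|---|---|
| Power | 2.0% | 2.8% | 5.4% |

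No threshold that Holm can offer makes this claim likely. The relevant case therefore has test 1 close to null and the other two effects real.

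**4. Gain with two real effects.** The documents give no effect sizes for the Grade 2+ and EPIC tests, so power *b* at 0.0167 is assumed to be 50, 70 or 80%. Normal approximation, independent tests:

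- Non-centrality = 2.394 + z(*b*), which is 2.394, 2.918 and 3.236.
- Power at two-sided 0.025 is *c* = Φ(non-centrality − 2.241) = Φ(0.153), Φ(0.677) and Φ(0.994), or 0.561, 0.751 and 0.840.
- Leaving test 1 aside, a claim is won under Holm if its p is at most 0.0167, or lies between 0.0167 and 0.025 while the other real test is at most 0.0167. The probability is *b* + (*c* − *b*)*b*:
  - 0.50 + 0.061 × 0.50 = 0.53
  - 0.70 + 0.051 × 0.70 = 0.74
  - 0.80 + 0.040 × 0.80 = 0.83
- Both real claims are won with probability *b*² under Bonferroni (0.25, 0.49, 0.64) and *c*² − (*c* − *b*)² under Holm (0.31, 0.56, 0.70). Occasional rejections of the near-null test add about one point to the chance of at least two claims.

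Simulation with all three tests agrees:

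| Assumed power at 0.0167 | Per claim under Holm | At least two claims, Bonferroni | At least two claims, Holm |
|---|---|---|---|
| 50% | 53% | 26% | 32% |
| 70% | 74% | 50% | 57% |
| 80% | 83% | 65% | 71% |

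**5. At least one claim.** This is unchanged, because Holm's first step is the Bonferroni threshold. With test 1 near its planning rates and the others at 80%, it is 96% under both rules.

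**6. If only the SAP's two listed tests stand.** The fixed threshold then spends 2 × 0.0167 = 0.033 of the 0.05, and plain Bonferroni would allow 0.025 each. A Grade 2+ test with assumed power of 80% at 0.0167 has 84.0% at 0.025 and 89.9% at 0.05. Holm's further gain over 0.025 depends on test 1 being won first: 0.840 + (0.899 − 0.840) × 0.028 = 0.842. In that case nearly all the benefit comes from counting the tests correctly.

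**7. The family is not fixed.** SAP 10.3.5.1 analyses EPIC in four domains, and none is named as the labelling test. Four domains plus the two Fisher tests at 0.0167 each would have a familywise bound of 6 × 0.0167 = 0.10. The Grade 2+ test also has two definitions: SAP 10.2 requires a rectal event that is also related and counts IMRT-related events, while SAP 10.3.5.1 joins the criteria with *or* and omits IMRT.

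**The case against.** The strongest reply is that this is a preference. Bonferroni is valid, prespecified and set at the same level in both documents. The tests are gated, so nothing about study success depends on them. Bonferroni also has simple matching simultaneous confidence intervals, and Holm does not. All of this stands, except that the interval advantage is unused: the plan specifies no multiplicity-adjusted intervals for these tests.

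The gain may also be smaller than in the table. If the two real tests have assumed power of 20% and 80%, Holm moves them only to 24% and 81%. The Grade 2+ test could well be weak: assumed rates of 10% v 5% give 12% power at 0.0167. The normal approximation also ignores the discreteness of the two Fisher tests.

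A reader might infer three stronger points that the documents do not support:

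- *That power per claim would rise from 80% to 86–88%.* This needs all three effects to be real, which conflicts with the planning rates of 19% v 21% for test 1. The definition in SAP 10.3.4.1.1 makes superiority there harder still, because qualifying events must be related to the device, the marking or the balloon implantation, and control men have the marking only.
- *That these tests are the only comparison with the randomised control.* The co-primary safety test is itself such a comparison, for non-inferiority. The labelling tests add superiority.
- *That Holm always rejects more.* It does so only when one p-value is at most 0.0167 and another falls in a wider band.

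**Conclusion.** The point holds as a low-cost efficiency improvement. The fixed 0.0167 is not an error. Holm meets the SAP's own 0.05 aim, cannot lose a claim that Bonferroni would win, and leaves the chance of at least one claim unchanged. With two real effects the gain is about 3 to 4 points per claim and 6 to 7 points in the chance of at least two claims. These sizes rest on assumed power of 50 to 80% for the Grade 2+ and EPIC tests, independence and a normal approximation; only the roughly 2% power of test 1 follows from the documents' own rates. The mismatch between three tests announced and two listed in SAP 10.2 matters more than the choice of procedure, because either procedure needs a fixed family.

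**What to change.** Make both changes before outcome data are unblinded.

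1. Settle the family in SAP 10.2. Either restore the protocol's EPIC genitourinary test on the last IMRT day, with one prespecified score, or state that there are two tests. Give the Grade 2+ test one definition in SAP 10.2 and 10.3.5.1.
2. In SAP 10.2 and Protocol 2.3.3, replace the fixed 0.0167 with Holm's procedure at two-sided familywise 0.05 over the listed tests: 0.0167, 0.025 and 0.05 for three tests, or 0.025 and 0.05 for two. Keep the gate on both co-primaries.

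The Holm change is one sentence in each document and needs no extra subjects or data. Settling the family takes more thought, but Bonferroni needs it as well. The one statistical cost is the lack of simple matching simultaneous intervals; Bonferroni-level intervals (98.3% for three tests) can still be reported.

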#### **10.3** Evaluations and Statistical Analyses

#### **10.3.1 Subject Disposition**

Subject disposition will include the total number of subjects screened and number of screen failures recorded in the database, which will include any patient who consented to participate whether they failed eligibility or withdrew prior to marking.

Subject follow-up will be summarized by treatment arm at baseline, marking/implantation, postimplantation, 6 months and every 6 months thereafter during the study. For each period, expected followup will be calculated as the number of subjects theoretically reaching that period, minus the number of subjects not yet overdue for that visit and minus any deaths occurring since the last visit. Actual followup for each period will be summarized by frequency and the percentage of expected follow-up. The frequency and percentage of subjects missing a visit window and/or discontinuing the study will be included, along with the reasons for discontinuation.

Study enrollment by location (US and outside US) and by each site will be summarized by the number and percentage of subjects.

#### 10.3.2 Demographics and Baseline Characteristics

Demographic and baseline information will be summarized for the PP population using descriptive statistics. Categorical variables (gender, race, clinical stage at baseline) will be summarized using frequency and percentages. Numeric variables (age, height, weight, BMI, AUA Symptom Score at baseline) will be summarized using descriptive statistics as total number of subjects surveyed (N), mean, median, standard deviation, minimum, maximum, and inter-quartile range.

The homogeneity of the baseline characteristics of the two randomized groups will be evaluated using Fisher's Exact Test, Likelihood Ratio chi-square tests, or Rank-Sum tests.

Medical history will be listed and will include descriptions of prior conditions and treatments, especially if related to the prostate, bladder, rectum, anus, or perineal area; and current medications and other drug

Statistical Analysis Dlan	Client/Project	BioProtect BP-007
Statistical Analysis Plan	Version and Date	V2 05-DEC-2021

therapies indicated for treatment of prostate cancer. The overall number and percentage of subjects with one or more medical history findings by type will be summarized.

#### **10.3.3 Procedure Information**

Procedure information will be summarized for the per protocol population.

Descriptive statistics in the form of frequencies and percentages will be provided related to the marking/implantation procedures, including the method of marking, ease of marking, dissection method, ProSpace positioning success, ease of instrumentation use, ease of implantation, and problems revealed by digital rectal exam (DRE).

#### 10.3.4 Co-Primary Endpoints and Analyses

This study has co-primary endpoints for safety and efficacy.

#### 10.3.4.1 Co-Primary Safety Endpoint and Analysis

#### 10.3.4.1.1 Primary Safety Endpoint

The adverse events qualifying as primary safety events will be determined through adjudication by the CEC. The primary safety endpoint is based on the occurrence of one or more adverse event as follows, as indicated on the CEC CRF:

- Event is indicated to be a Grade 1 or greater rectal event lasting at least 2 days through the first 183 days (6 months) and
- Event meets one of the relatedness classifications:
  - Event is indicated to possible, probably, or definitely device-related;
  - Event is related to marking or
  - Event is related to the balloon implantation procedure.

Note that events related to anesthesia or to the use of a foley catheter will not be considered marking or implantation procedure-related.

Subjects will be counted as having an event if one occurs anytime through Day 183 (6 months) from the marking date or as not having an event if they record no events and are followed through at least Day 169 (6 month minus 14 days) from the marking date. Subjects who terminate the study before Day 169 and did not experience the AE of interest will be considered missing from the PP population and not included in the primary safety analysis. The impact of these subjects will be evaluated in a sensitivity analysis for the primary safety endpoint as described below.

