2.2.2.3 PRIMARY SAFETY ENDPOINT

The primary safety endpoint is the rate of occurrence of Grade 1 or greater rectal adverse events and implantation procedure related adverse events with a duration of at least 2 days through 6 months. This rate will be compared between the balloon group and the control group, and the study will be considered a success if statistical significance is achieved on a one-sided non-inferiority test. Details appear in **Section 2.3**.

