2.3.4.1 PRIMARY SAFETY ANALYSES

The primary safety endpoint is based on the occurrence of Grade 1 or greater rectal adverse events and implantation procedure related adverse events with a duration of at least 2 days through the first six months. Subjects will be counted as having an event if one occurs anytime through Day 197 from the marking date (6 months plus up to 14 days) or as not having an event if they record no events and are followed for at least Day 169 (6 month minus 14 days) from the marking date. A one-sided test of non-inferiority will be completed using the Farrington-Manning method with a non-inferiority bound of 15%. If we denote the s_{pr} to the safety event rate in the *balloon Group* and s_c to be the safety event rate in the *Control Group*, the hypothesis is as follows:

$$H_0: \, s_{pr} - s_c \geq 0.15 \ vs \ H_1: \ s_{pr} - s_c < 0.15$$

The study will be a success if the test is significant against a one-sided p-value cut-off of 0.025.

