2.3.6 RISK ANALYSIS

Following is a list of potential adverse events for this study. These include events that have been identified by nature, severity, or frequency in the current literature or in the investigational plan.

2.3.6.1 **RISKS**

Risks associated with the use of the BioProtect Balloon Implant System in conjunction with the control procedure (marking and IMRT) are expected to be comparable to the risks associated with the control procedure alone. *Risks associated with radiation therapy include:*

- Acute urinary retention (usually related to general anesthesia administration);
- Bladder neck constriction or stricture;
- Fatigue;
- Fragility fractures (if hormone use is added to the treatment);
- Hemospermia (blood in the sperm);
- Hot flashes (if hormone use is added to the treatment);

- Erectile dysfunction;
- Pruritis;
- Radiation cystitis or urethritis;
 - o Bladder spasms,
 - Burning with urination,
 - Dysuria (difficulty emptying bladder),
 - Hematuria (blood in the urine),
 - Nocturia (need to urinate during sleeping hours),
 - Urgent, frequent urination.
- Radiation enteritis;
 - o Gas,
 - Bowel urgency,
 - Abdominal pain,
 - Abdominal tenderness.
- Rectal-anal mucositis (irritation and ulceration);
- Radiation proctitis and other rectal side-effects;
 - Burning with bowel movements,
 - o Diarrhea,
 - Hematochezia (blood in the stool),

- Loose stools.
- Rectal bleeding,
- Rectal fistula,
- Rectal ulcer,
- Straining.

- o Hemorrhoids,
- Tenesmus (feeling of incomplete defecation);
- Urinary incontinence;
- UTI;
- Vasovagal episode (usually caused by severe straining).

Risks associated with marking and/or spacer implantation procedure include:

- Fever greater than 100°;
- Site bleeding mild to moderate;
- Site hematoma temporary, self terminated;
- Site infection and related symptoms Infection along the trajectory of the insertion of surgical tools, including the site of implantation;
- Rectal wall puncture.

Risks specifically associated with the BioProtect Balloon Implant Systeminclude:

- Erosion through a hollow organ wall such as bowels, urinary bladder, etc.;
- Incomplete absorption;
- Inflammatory reaction;
- Migration of the device from the desired location;

- Needle penetration into bloodstream, bladder, prostate, rectal wall, rectum or urethra;
- Premature balloon deflation;
- Prolonged or delayed procedure;
- Rectal perforation;
- Tissue necrosis.

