While it is advantageous to treat prostate cancer with the highest feasible dose, it is currently avoided by most therapy centers due to the fact that higher dosage to the prostate will eventually result in higher dosage to the rectum. Inserting the balloon in situ between the prostate and the rectum will enable admission of higher dosage whether as total (accumulative) or per session (hypofractionation) or both, potentially reducing acute and late and chronic rectal toxicity.

The rectal toxicity of conventional radiation therapy (XRT) and even the current focused XRT machinery and methods (3D- CRT, IMRT and IGRT), and the hypofractionation trend, potentially can be reduced as lesser radiation at any given dose to the prostate will eventually reach the rectum. Grade 2-3 late and chronic toxicity ranges from 5 to 20 % and more (in particular with hypofractionation). The adverse event rate (Grade 1 events) for the Augmenix SpaceOAR was 34% (DEN140030).

The potential reduction of radiation to the rectum at any given radiation dose to the prostate will potentially reduce acute rectal toxicity, which in turn may reduce the late and chronic rectal toxicity.

The assumed potential risk of using the BioProtect Balloon Implant Systemis mainly the potential risk for rectal perforation and from injury during the implantation procedure. It should be noted however, that unlike the late complications associated with high-dose radiation that are chronic and may take years for resolution, this potential risk is temporary and reversible. Nevertheless, the potential risk of rectal perforation is mitigated by the following actions:

- 1. The entire procedure will be done with the guidance of Trans Rectal Ultra Sound (TRUS); and the user will be a well-trained urologist or physician that is familiar with the brachytherapy transperineal approach using TRUS.
- 2. The user will be well trained by the company to the specific implantation procedure with relation to the anatomy. This will be done by thorough reading of the IFU, simulating the implantation on a phantom model using TRUS, explanation of videos showing the phantom simulation and human real case simulation, and supervising the initial cases as needed, by a company trained physician.
- 3. The delivery system uses a spinal needle type, which is blunt at the tip.

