#### 10.3.5.1 Secondary Safety Endpoints

#### Secondary Safety Endpoint #1: Grade 2 Adverse Events

As with the primary safety endpoint, the adverse events qualifying for this secondary safety endpoint will be determined through adjudication by the CEC. This secondary safety endpoint is based on the occurrence of one or more adverse event as follows, as indicated on the CEC CRF:

- Event is indicated to be a Grade 2 or greater Rectal event lasting at least 5 days through the first 183 days (6 months) or
- Event meets one of the relatedness classifications:
  - Event is indicated to possible, probably, or definitely device-related;
  - Event is related to marking or
  - Event is related to the balloon implantation procedure.

As with the primary safety endpoint, subjects will be counted as having an event if one occurs anytime through Day 183 (6 months) from the marking date or as not having an event if they record no events and are followed through at least Day 169 (6 month minus 14 days) from the marking date. This analysis will be based on the CEC classification as identified in Section 10.3.4.1.1. To compare the event rate of the *ProSpace Group* with that of the *Control Group*, the adverse event endpoint will be analyzed using a Fisher's exact test.

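### The 2-day minimum duration in the co-primary safety endpoint covers every grade, so a short Grade 3-4 rectal injury can be scored as no event, and no sensitivity analysis tests this

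*SAP*

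**What the plan says.** **Co-primary safety endpoint.** Protocol 2.2.2.3 sets the rule as events "with a duration of at least 2 days through 6 months". Protocol 2.3.4.1 repeats it, with the period given in months: "Grade 1 or greater rectal adverse events and implantation procedure related adverse events with a duration of at least 2 days through the first six". SAP 10.3.4.1.1 words the criterion as "Event is indicated to be a Grade 1 or greater rectal event lasting at least 2 days through the first 183 days (6 months) and", followed by the need for a device, marking or implantation relationship as adjudicated by the Clinical Events Committee (CEC). Severity is graded 1 to 5 under CTCAE (protocol 2.3.5.1), but none of these definitions varies the minimum duration by grade.

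**Who is scored as no event.** SAP 10.3.4.1.1 requires no qualifying event and follow-up to at least Day 169. A subject who leaves earlier without a qualifying event is treated as missing.

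**Stated risk.** The protocol's risk-benefit discussion (before 2.3.8) describes the device risk as "mainly the potential risk for rectal perforation and from injury during the implantation procedure". Among risks specific to the balloon system, protocol 2.3.6.1 lists "Needle penetration into bloodstream, bladder, prostate, rectal wall, rectum or urethra".

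**Sensitivity analyses.** SAP 10.3.4.1.3 plans a Day 197 version, a tipping-point analysis and Kaplan-Meier estimates.

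**Grade 2 endpoint.** SAP 10.2 requires a relationship that may be device, "marking/implantation procedure-related, or IMRT-related with a duration of at least 5 days will be evaluated using a two-sided Fisher's Exact test". SAP 10.3.5.1 instead has "Event is indicated to be a Grade 2 or greater Rectal event lasting at least 5 days through the first 183 days (6 months) or" a relatedness condition.

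**The concern.** A minimum duration is a sensible way to keep passing mild symptoms out of a Grade 1 endpoint. Applied to every grade, it can order events against their clinical weight. Two days of Grade 1 rectal symptoms that the CEC links to the device or procedure make a subject an event. A related Grade 3 rectal injury recorded as found and resolved within a day does not.

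Short recorded durations are plausible for the injury the protocol worries about most. The protocol calls the risk temporary and reversible. It looks for rectal injury during the procedure, by palpation before inflation and by a digital rectal examination at the end, with anuscopy if injury is suspected. Neither document says how duration is calculated or when a puncture counts as resolved.

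At stake is the claim that the balloon is non-inferior on safety, and also the labelling test of superiority on the same endpoint (protocol 2.3.3, SAP 10.2), which inherits the definition. The omission probably favours the balloon, because dissection and balloon delivery occur only in that arm.

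**Working it through.** **1. Does any planned analysis relax the duration rule?**

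| Analysis (SAP) | What it changes | Event definition |
|---|---|---|
| Primary (10.3.4.1.2) | – | 2-day minimum, all grades |
| Day 197 (10.3.4.1.3) | Time window | Same |
| Tipping point (10.3.4.1.3) | Values for missing subjects | Same for observed subjects |
| Kaplan-Meier (10.3.4.1.3) | Handling of follow-up time | Same: time to primary safety event |

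None does. Short high-grade events would be seen only in descriptive output: the adverse event tables by grade, severity, seriousness and relationship, and the examination findings in 10.3.3.

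**2. The plan's own power figure.** Inputs from protocol 2.3.4.4: 68 control and 136 balloon subjects, rates 21% and 19%, margin 0.15, one-sided alpha 0.025, Farrington-Manning test.

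- The restricted maximum-likelihood rates under a difference of 0.15 are 0.2717 (balloon) and 0.1217 (control).
- SE0 = √(0.2717×0.7283/136 + 0.1217×0.8783/68) = 0.0550.
- SE1 = √(0.19×0.81/136 + 0.21×0.79/68) = 0.0598.
- Power = Φ[(0.15 + 0.02 − 1.96×0.0550)/0.0598] = 85.1%. Exact enumeration gives 86.0%.

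The stated 85% is reproduced, so there is no numerical error here.

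**3. Weight of one subject.** 1/136 = 0.74 percentage points, and 3/136 = 2.2 points. This applies only to a man with no other qualifying event, because the endpoint counts subjects.

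**4. How many would change the verdict?** The planned rates correspond to about 14/68 (20.6%) and 26/136 (19.1%). With z = (balloon rate − control rate − 0.15)/SE0 and control fixed at 14/68:

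| Balloon events | Difference | SE0 | z | One-sided p |
|---|---|---|---|---|
| 26/136 | −0.0147 | 0.0549 | −3.00 | 0.001 |
| 30/136 | 0.0147 | 0.0566 | −2.39 | 0.008 |
| 32/136 | 0.0294 | 0.0574 | −2.10 | 0.018 |
| 33/136 | 0.0368 | 0.0578 | −1.958 | 0.0251 |

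The test passes up to 32 and fails from 33. Starting from 26, that takes 33 − 26 = 7 additional balloon subjects, or 7/136 = 5.1 points.

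**5. Illustration under assumed frequencies.** The documents give no rate for related Grade 3 or higher rectal events under 2 days. Suppose counting them adds q to the balloon rate only, from 19%, with control held at 21%. Expected subjects = 136q; chance of at least one = 1 − (1 − q)^136.

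| Assumed q | Expected subjects | Chance of ≥1 | Exact power when counted |
|---|---|---|---|
| 0 | 0 | – | 86.0% |
| 1% | 1.4 | 75% | 80.9% |
| 2% | 2.7 | 94% | 75.0% |
| 3% | 4.1 | 98% | 68.3% |

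If both arms rise equally, power is 84.6% at 1% and 83.1% at 2%.

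**6. The Grade 2 endpoint, side by side.**

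| Place | Duration rule |
|---|---|
| Protocol 2.3.3 | At least 5 days |
| Protocol 2.3.4.5 | At least 5 days, then procedure-related events named again with no duration |
| SAP 10.2 | Rectal and related, at least 5 days |
| SAP 10.3.5.1 | Rectal for at least 5 days, or related (no duration stated) |
| SAP Table 14.2.3 title | Two or more days |

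These definitions cannot all be applied.

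**The case against.** A uniform minimum is a stated design choice, and it is the same in both protocol sections and the SAP. Qualification rests on CEC adjudication, not on site dates alone. The events are not hidden: the SAP tabulates adverse events by grade, and device- and procedure-related severe and serious events by arm; unanticipated device effects are summarised too. The frequency is unknown, and at the planned rates a few extra subjects would not reverse the result. The control arm is exposed as well: both arms are marked transperineally, and protocol 2.3.6.1 lists rectal wall puncture under marking and/or spacer implantation.

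All of this stands, and it argues against replacing the agreed primary definition. It does not answer the narrower point. Descriptive tables lie outside the success criterion, and no planned analysis shows whether the safety conclusion depends on leaving short severe injuries out.

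A reader might infer more than the documents support:

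- *That the Grade 2 endpoint drops these injuries too.* This fits SAP 10.2 and protocol 2.3.3. Under the alternative wording in SAP 10.3.5.1, a device-, marking- or implantation-related injury counts at any duration. The defect there is the conflict between definitions.
- *That a rapidly fatal Grade 5 event scores as no event.* A man who dies before Day 169 without a qualifying event does not meet the follow-up condition. The wording for early termination points to missing, which the tipping-point analysis then varies. The SAP does not name deaths, but nothing in it scores an early death as no event.
- *That the CEC form already holds grade and duration.* The form is not in the documents, and the list of CEC characterisations in SAP 10.3.6.1 includes neither.

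**Conclusion.** The concern holds for the co-primary safety endpoint, within limits. It applies to a non-fatal Grade 3-4 rectal injury, related to device, marking or implantation, recorded as lasting under 2 days, in a subject followed to Day 169 with no other qualifying event. That subject is scored as no event, and no sensitivity analysis would show the effect.

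The direction is probably in favour of the balloon, but not certainly, since marking can injure the rectal wall in either arm. The size is 0.74 percentage points per uncounted balloon subject. With 14/68 control events, the verdict changes only from 33/136 balloon events. The 1-3% frequencies above are assumptions; they show scale and do not estimate how often such injuries occur.

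The gap concerns what the endpoint measures, given the protocol's own account of the main risk. It warrants a low-cost addition and does not invalidate the primary analysis. The conflicting Grade 2 definitions are a separate matter that needs resolving in its own right.

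**What to change.** Keep the agreed primary definition. Add to SAP 10.3.4.1.3, beside the Day 197 analysis, a named sensitivity analysis: repeat the Farrington-Manning test with the 15% margin, counting as events all subjects who meet the primary definition plus any subject with a CEC-adjudicated, related rectal event of Grade 3 or higher through Day 183, whatever its duration. First confirm that grade and duration are available, either to the CEC or from the adverse event data.

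Separately, reconcile the Grade 2 endpoint across protocol 2.3.3 and 2.3.4.5, SAP 10.2 and 10.3.5.1, and the title of Table 14.2.3. Decide at the same time how short high-grade events are handled there.

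The cost is one paragraph and one table, with no added patients or visits; the data check may need some work if the CEC form lacks these items. The downside for the sponsor is that the balloon rate in the sensitivity analysis may rise by one or a few subjects.
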